## 13.0 PARTICIPANTS

### 13.1 Institutional Review Board (IRB) Review and Informed Consent

This protocol and the informed consent documents (Appendices I-III) and any subsequent modifications will be reviewed and approved by the IRB or EC responsible for oversight of the study. A signed consent form will be obtained from the participant (or parent, legal guardian, or person with power of attorney for participants who cannot consent for themselves, such as those below the legal age of consent). The consent form will describe the purpose of the study, the procedures to be followed, and the risks and benefits of participation. A copy of the consent form will be given to the participant, parent, or legal guardian, and this fact will be documented in the participant's record.

### 13.2 Participant Confidentiality

All laboratory specimens, evaluation forms, reports, and other records that leave the site will be identified by coded number only to maintain participant confidentiality. All records will be kept locked. All computer entry and networking programs will be done with coded numbers only. Clinical information will not be released without written permission of the participant, except as necessary for monitoring by the ACTG, IRB/EC, FDA, NIAID, OHRP, or other local, US, and international regulatory entities as part of their duties.

### 13.3 Study Discontinuation

The study may be discontinued at any time by the ACTG, IRB/EC, FDA, NIAID, OHRP, or other country-specific government agencies as part of their duties to ensure that research participants are protected.

#### 14.0 PUBLICATION OF RESEARCH FINDINGS

Publication of the results of this trial will be governed by ACTG policies.

#### 15.0 BIOHAZARD CONTAINMENT

As the transmission of HIV and other blood-borne pathogens can occur through contact with contaminated needles, blood, and blood products, appropriate blood and secretion precautions will be employed by all personnel in the drawing of blood and shipping and handling of all specimens for this study, as currently recommended by the CDC and the National Institutes of Health.

All dangerous goods and materials, including diagnostic specimens and infectious substances, must be transported using packaging mandated by CFR 42 Part 72. Please refer to instructions detailed in the International Air Transport Association (IATA) Dangerous Goods Regulations.

## APPENDIX IV: PROHIBITED AND PRECAUTIONARY MEDICATIONS

**Some drugs on these lists that can be used topically may be allowed on a case-by-case basis, after discussion with and approval by the protocol team via e-mail as described in the [Study Management section](#).**

## 1.0 PROHIBITED MEDICATIONS

## 1.1 Other Hormones

All Groups: Efavirenz, Dolutegravir, Rifampicin

- Delestrogen
- Depotestrogen
- Desogestrel
- Drospirenone
- Estradiol cypionate
- Estradiol Valerate
- Estrogens, Conjugated
- Estrogens, Esterfied
- Ethinyl Estradiol
- Ethynodiol Diacetate
- Etonogestrel
- Gestodene
- Hydroxyprogesterone
- Levonorgestrel
- Medroxyprogesterone
- Norelgestromin
- Norethindrone
- Norgestimate
- Norgestrel
- Progesterone
- Testosterone

## 1.2 Other Concomitant Medications

Group A and B: Efavirenz

- Amodiaquine
- anticonvulsants (carbamazepine, Eslicarbazepine, felbamate, fosphenytoin, Lamotrigine, Oxcarbazepine, Perampanel, phenytoin)
- Astemizole
- Azole Antifungals (Fluconazole, itraconazole, ketoconazole, posaconazole, voriconazole)
- barbiturates (phenobarbital, primidone)
- Bepridil
- cat's claw

- Cisapride
- dexamethasone
- Dihydroergotamine
- Enzalutamide
- Ergotamine
- Griseofulvin
- integrase strand transfer inhibitors (including dolutegravir, elvitegravir, raltegravir, bictegravir)
- Macrolides (Clarithromycin, erythromycin)
- maraviroc
- Midazolam
- Mitotane
- Other Nonnucleoside reverse transcriptase inhibitors (including nevirapine, rilpivirine, delavirdine, doravirine)
- Protease inhibitors (HIV or HCV)
- Rifamycins (including rifampin, rifapentine & rifabutin)
- St John's Wort
- Terfenadine

#### Group C: Dolutegravir

- African potato
- anticonvulsants (carbamazepine, Eslicarbazepine, felbamate, fosphenytoin, Lamotrigine, Oxcarbazepine, Perampanel, phenytoin)
- Azole Antifungals (Fluconazole, itraconazole, ketoconazole, posaconazole, voriconazole)
- barbiturates (phenobarbital, primidone)
- Dofetilide
- Enzalutamide
- Macrolides (Clarithromycin, erythromycin)
- maraviroc
- Mitotane
- Nonnucleoside reverse transcriptase inhibitors (including efavirenz, nevirapine, rilpivirine, delavirdine, doravirine)
- Other integrase strand transfer inhibitors (including elvitegravir, raltegravir, bictegravir)
- protease inhibitors (HIV or HCV)
- Rifamycins (including rifampin, rifapentine & rifabutin)
- St John's Wort

#### Group D: Rifampicin

- anticonvulsants (carbamazepine, Eslicarbazepine, felbamate, fosphenytoin, Lamotrigine, Oxcarbazepine, Perampanel, phenytoin)
- Azole Antifungals (Fluconazole, itraconazole, ketoconazole, posaconazole, voriconazole)
- barbiturates (phenobarbital, primidone)

- Enzalutamide
- Halothane
- integrase strand transfer inhibitors (including dolutegravir, elvitegravir, raltegravir, bictegravir)
- Macrolides (Clarithromycin, erythromycin)
- maraviroc
- Mitotane
- Nonnucleoside reverse transcriptase inhibitors (including efavirenz, nevirapine, rilpivirine, delavirdine, doravirine)
- Other Rifamycins (rifabutin & rifapentine)
- protease inhibitors (HIV or HCV)
- St. John's Wort

## 2.0 PRECAUTIONARY MEDICATIONS

### Groups A and B: Efavirenz

- Aprepitant
- Artemether/lumefantrine
- Atovaquone/proguanil
- Azole antifungals (itraconazole, posaconazole)
- Bosentan
- clopidogrel
- diltiazem
- Fosaprepitant
- garlic
- ginkgo biloba
- GLP-1 agonists (exenatide, lixisenatide)
- hops
- Lesinurad
- malabar nut tree
- Mycophenolate
- nefazodone
- pioglitazone
- Proguanil
- Prucalopride
- quercetin
- Telithromycin
- ticlopidine
- Topiramate
- Triazolam

### Group C: Dolutegravir

- antacids - follow product labeling for instructions on separation with DTG
- Aprepitant
- Artemether/lumefantrine

- buffered medications - follow product labeling for instructions on separation with DTG
- divalent cations (e.g., Ca++, Fe++) - follow product labeling for instructions on separation with DTG
- Fosaprepitant
- garlic
- GLP-1 agonists (exenatide, lixisenatide)
- Lesinurad
- malabar nut tree
- MVI - follow product labeling for instructions on separation with DTG
- Mycophenolate
- Prucalopride
- sucralfate - follow product labeling for instructions on separation with DTG
- Topiramate

Group D: Rifampicin

- antacids - follow product labeling for instructions on separation with RIF
- Aprepitant
- Artemether/lumefantrine
- cotrimoxazole
- Fosaprepitant
- GLP-1 agonists (exenatide, lixisenatide)
- Lesinurad
- Mycophenolate
- probenecid
- Prucalopride
- Topiramate

1.1 Purpose

This Primary Statistical Analysis Plan (SAP) describes the primary and secondary outcome measures and any additional outcome measures of the ACTG A5375 study that will be included in the primary manuscript, and which address, at a minimum, the major primary and secondary objectives of the study. The Primary SAP outlines the general statistical approaches that will be used in the analysis of the study. It has been developed to facilitate discussion of the statistical

analysis components among the study team, and to provide agreement between the study team and statisticians regarding the statistical analyses to be performed and presented in the Primary Analysis Report. It also describes the results for the primary and secondary outcome measures that will be posted on ClinicalTrials.gov.

Detailed outlines of tables, figures, and coding descriptions that will be included in the Primary Analysis Report are included in the Analysis Implementation Plan (AIP).

Analyses for the Primary Analysis Report will be finalized once the last participant has completed the study, all queries have been resolved, and the study database closure/data lock has been completed.

1.2 Version History Table

Version	Changes Made	Rationale	Effective Date
1	Original Version		09/10/2019
2	Addition of SMC letter recommendation about PK replacement and edits based on team discussion/consensus Edits to PK data imputations based on assay limits	Review/update of SAP done in preparation for study closure based on said timeline	07/24/2020
3.0	Minor formatting changes, correction of typo, and other minor updates to align with protocol version 2. Attachment 2 : timeline was updated to reflect current forecasting near time of primary analysis initiation Removal of contingency language to perform primary analysis in 2 stages based on observed prompt completion of accrual. Reversing ratio for secondary comparison of groups A versus B so that Group A is in the denominator of the GMR. Refining definition of other outcome measure – single timed concentration of RIF and associated metabolites, to reflect testing of earlier post RIF dose samples due to accelerated clearance of RIF. And updating the thresholds for exclusion of participants in secondary analyses due to inadequate perpetrator drug concentrations.	Review triggered by finalization and release of protocol version 2 (dated 10/30/2020)	05/24/2021

	
Addition of sensitivity analysis to the primary PK (for the assumption of equal variance between groups), as well as supplementary analyses to explore the robustness of primary PK analyses: a) exclusion of participants with inadequate measured exposure to perpetrator drug , and b) calculation of adjusted GMRs to account for imbalance in prognostic factors between comparison groups.
		
--	---	--	--

2 Study Overview

2.1 Study Design

Copied from v2 (10/30/2020) Protocol Schema:

DESIGN

A5375 is a phase II, open-label, four parallel group, partially randomized, pharmacokinetic (PK) study to evaluate if a double dose of levonorgestrel (LNG) emergency contraception (EC) overcomes known drug-drug interactions (DDIs) with efavirenz (EFV)-based antiretroviral therapy (ART) or rifampicin (RIF)-containing tuberculosis (TB) therapy. The safety of double-dose LNG EC versus standard-dose will also be compared.

Participants will be volunteers who do not currently require EC for contraception. Eligible participants will receive a single dose (1.5 mg) or a double dose (3.0 mg) of LNG EC based on their group assignment, which will be determined by their infection (HIV or TB; participants cannot be coinfectd), and, for those who are living with HIV, by their ART regimen at enrollment (see Schema Figure 1). Women living with HIV who are taking EFV-based ART will be randomized to Group A or B (1:2 ratio). Women taking dolutegravir (DTG)-based ART will be assigned to Group C. Women who are HIV-negative and in the continuation phase of TB treatment taking RIF and isoniazid (INH) will be assigned to Group D.

DURATION

All participants will be followed for 4 weeks.

SAMPLE SIZE

116 participants; 17 in Group A, 33 in each of Groups B, C, and D.

POPULATION

Women who are 16 years of age or older, and who are either HIV+ and on stable ART, or who are HIV- and in the continuation phase of anti-TB therapy on daily INH/RIF.

STRATIFICATION

[figure not shown]
At entry, women with body mass index (BMI) ≥ 30 kg/m² will be limited to no more than five within Groups B-D and no more than three within Group A.

REGIMEN

Women in Groups A and C will receive 1.5 mg LNG EC once at study entry.

Women in Groups B and D will receive 3.0 mg LNG EC once at study entry.

Schema Figure 1: Study Design

Hypotheses (copied from protocol v2):

2.1.1 Primary Hypotheses:

- 1) *Women receiving double-dose levonorgestrel (LNG) emergency contraception (EC) with efavirenz (EFV)-based antiretroviral therapy (ART) will achieve similar LNG concentrations compared to women receiving standard-dose LNG EC on dolutegravir (DTG)-based ART.*
- 2) *Women receiving double-dose LNG EC with rifampicin (RIF)-containing tuberculosis (TB) therapy will achieve similar LNG concentrations compared to women receiving standard-dose LNG EC on DTG-based ART.*

2.1.2 Secondary Hypotheses:

- 1) *Among women receiving EFV-based ART, double-dose LNG EC will achieve significantly higher LNG concentrations than standard-dose LNG EC.*
- 2) *Women receiving standard-dose LNG EC with EFV-based ART will achieve significantly lower LNG concentrations than women receiving standard-dose LNG EC on DTG-based ART.*
- 3) *Double-dose and standard-dose LNG EC will have similar safety profiles.*

2.2 Study Objectives

This Primary SAP addresses the following primary and secondary objectives listed in the study protocol. Other study objectives in the protocol will be addressed in subsequent analysis plans.

Inference framework varies by objective/hypothesis above, and some comparisons rely on interpretation of confidence intervals rather than hypothesis testing. Because there is not a single framework across the analysis, these details will be provided by outcome below.

Objectives (copied from protocol v2):

2.2.1 Primary Objectives

- 1) *To determine if doubling the dose of the LNG EC effectively overcomes the known drug-drug interaction (DDI) with EFV-based ART.*
- 2) *To determine if doubling the dose of the LNG EC effectively overcomes the expected DDI with RIF-containing TB therapy.*

2.2.2 Secondary Objectives

- 1) *To estimate the difference in LNG pharmacokinetic (PK) exposure with double-dose LNG EC compared to standard-dose LNG EC in women receiving EFV-based ART.*
- 2) *To estimate the difference in LNG PK exposure with standard-dose LNG EC in women receiving EFV-based ART compared to women receiving DTG-based ART.*

- 3) *To verify the absence of significant DDI between LNG EC and DTG-based ART.*
- 4) *To compare the safety of double-dose LNG EC compared to standard-dose LNG EC.*
- 5) *To evaluate the relationship between baseline measures of body weight (body fat percentage, total weight, and body mass index [BMI]) and LNG PK exposure.*

2.2.3 Exploratory Objectives

- 1) *To characterize the relationship between short- and long-term adherence to ART or TB therapy and LNG exposure using objective pharmacologic measures. [Note: only short-term adherence will be assessed in the primary analysis, via measured concentrations of targeted ART or TB medications.]*

2.3 Overview of Sample Size Considerations

Given that a therapeutic target for minimum exposure required or average exposure expected for single dose use of LNG as emergency contraception (EC) is unknown, this study is estimating whether adjusted dosing of LNG under a known DDI achieves similar exposure to LNG single dose as measured by the geometric mean ratio (GMR) of the AUC of LNG concentrations over the 8 hours post dose.

Assuming 30 women per comparison group, coefficient of variation of AUC(LNG0-8hr)= 0.45 {and standard deviation on 0.429 of AUC(LNG) as calculated from CV using the formula square root of $[\ln(CV^2+1)]$ }, and significance level 10% (corresponding to inverting 2 one-sided tests, each at 5% significance), then under true GMR=100%, there is 88% statistical power for declaring similarity in LNG exposure between groups using No-Effect Bounds of (70%,143%). Under similar assumptions, a 90% 2-sided confidence interval (calculated as median LCB and UCB from simulations), about a true GMR=100% ranges over (83%, 120%). Final sample sizes for accrual goals were inflated by 10% to protect against losses to follow-up.

The protocol document has further details on sample size justification.

Note that information above has been copied from the protocol. For analysis and reporting purposes, it has been decided to report GMR on the ratio scale (where 1=equivalence rather than 100%), and so the No-Effect Bounds in the analysis sections below use adjusted scaling to match the GMR scale for analysis and reporting.

2.4 Overview of Formal Interim Monitoring

2.4.1 Timing of reviews

This study will be formally monitored at least annually by an ACTG network-appointed SMC. The first interim review will occur no more than one year after the enrollment of the first participant or approximately 3 months after 25 women have completed the study, whichever occurs earlier. An additional SMC review may be triggered if the accrual at one year is less than 50% of total expected accrual. The protocol provides further details on an interim review triggered by slow accrual. An unplanned interim review will be triggered if, at any time, any participant experiences an SAE that is attributed to LNG (by adjudication by the core team and DAIDS clinical

representative), or if more than five women need to be replaced in the PK analysis set (see protocol section 9.2).

Note: Eligibility and enrollment issues that cause participant replacement will not be included in the above limit of 5 women.

2.4.2 Scope of reviews

There are no plans to initiate PK testing prior to initiation of the primary and/or final analysis, and thus there are no planned early looks or interim analysis of the primary efficacy outcome, or related outcomes calculated from PK concentrations. Therefore, the scope of interim reviews will be study conduct and safety.

3 Outcome Measures

Note: Outcome Measure information in italics inside boxes reflects the clinicaltrials.gov record specifications. Even though some secondary outcomes below are evaluated after the PCD, because study duration is only one month, we anticipate that all primary and secondary outcomes will be reported with the initial clinicaltrials.gov results submission.

3.1 Primary Outcome Measures

Title: LNG PK Parameter Area under the concentration-time curve (AUC0-8h) calculated based on intensive LNG PK samples obtained from individual participants

Description: AUC for each participant will be calculated from LNG concentrations measured over 8 hours using the linear up/log down version of the trapezoidal rule (i.e., noncompartmental technique) using the software package Phoenix WinNonLin (Certara®). This version of the trapezoidal rule uses linear interpolation between untransformed data up to C_{max} , and between log-transformed data from C_{max} through C_{last} . Assay lower limit of quantification for LNG was 0.025 ng/mL; values < LLOQ were imputed as 0 (if pre-dose) or as 0.125 (if post-dose)

Time Frame: Intensive LNG PK samples within 30 minutes pre-dose, and at 0.5, 1, 1.5, 2, 3, 4, 6, and 8 hours post-dose

Analysis Population: Participants with PK concentrations over 8 hours post LNG dose and who took both assigned dose of LNG study treatment and expected doses of ART or TB therapy

Reporting Groups: A-D

Associated Study Objective: Primary Objectives 1 and 2, Secondary Objectives 1 and 2 (see table below for more details)

Summary Statistics per group (those in italics included in clinicaltrials.gov results record):

- **Original scale (ng*h/mL, mcg*h/mL as reported by testing lab):** n, mean, sd, CV, *median*, IQR (Q1, Q3), Range (min, max)
- **Natural log scaled:** geometric mean, 95% CI on GM

Descriptive analysis will include the following:

- a) LNG concentration-time plots will be provided to inform the derivation of the primary AUC outcome and other PK parameters (secondary outcomes)

Statistical Analysis Summary:

DTG is not expected to alter LNG PKs. Because DTG is not expected to have DDIs with LNG, Group C (DTG) acts as a control arm for certain comparisons stated in the table below.

Note 1: GMR presented on ratio scale where equivalence is 1 (and not 100%).

Note 2: The Exact reference groups require additional specification of the key other med (ARV/TB med). Group codes are given for redundancy.

Statistical Analysis	Comparison Group selection	Type of Statistical Test	Estimation Parameter	Confidence Interval	Comments

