### 11.3 Primary and Secondary Data, Modeling, and Data Analysis

#### LNG analysis

The PK parameters for LNG include: maximum concentration ( $C_{max}$ ), time to maximum concentration ( $T_{max}$ ), minimum concentration ( $C_{min}$ ), **time to minimum concentration ( $T_{min}$ )**, oral clearance (CL/F), volume of distribution (Vd), elimination half-life ( $T_{1/2}$ ), and area under the concentration-time curve over 8 hours ( $AUC_{0-8h}$ ), 24 hours ( $AUC_{0-24h}$ ), 48 hours ( $AUC_{0-48h}$ ), and to infinity ( $AUC_{inf}$ ). Standard noncompartmental techniques will be used to determine these PK parameters using the software package Phoenix WinNonLin (Certara®). The AUC (including the primary outcome) will use the linear up/log down version of the trapezoidal rule. This version of the trapezoidal rule uses linear interpolation between untransformed data up to  $C_{max}$ , and between log-transformed data from  $C_{max}$  through  $C_{last}$  [81, 82].  $C_{max}$  will be taken as the maximum observed concentration.  $T_{max}$  is the time at which  $C_{max}$  occurs.  $C_{min}$  will be taken as the minimum observed concentration after the observed dose. Apparent oral clearance will be calculated as  $CL/F = \text{dose}/AUC_{0-24}$  or  $CL/F = \text{dose}/AUC_{0-48}$ . The  $T_{1/2}$  will be determined using regression analysis when possible.

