#### Hair analysis

Hair levels will be evaluated as continuous variables, possibly using logarithmic transformation if their distribution is skewed. Values below the detection limit will be counted as equal to the detection limit. We will examine scatterplots and calculate Spearman correlation coefficients for hair levels with plasma concentrations, we will also examine the correlation between SNPs in the genes implicated in EFV metabolism (e.g., CYP2B6) and hair concentrations of EFV.

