3.2.2 Secondary LNG PK Parameters

Title: LNG PK Parameters calculated based on intensive LNG PK samples obtained from individual participants

Descriptions:

Note: Unless otherwise indicated, standard noncompartmental techniques were used to determine the PK parameter using the software package Phoenix WinNonLin (Certara®).

C_{max}: C_{max} for each participant was the maximum observed concentration.

C_{min}: C_{min} for each participant was the minimum observed concentration after the observed dose among post-dose concentrations. Assay lower limit of quantification for LNG was 0.025 ng/mL; values < LLOQ were imputed as 0.0125.

CL/F: Apparent oral clearance (CL/F) was calculated from the observed LNG concentration from LNG PK samples at pre-dose through 48 hours post-dose. Assay lower limit of quantification for LNG was 0.025 ng/mL; values < LLOQ were imputed as 0 (if pre-dose) or as 0.0125 (if post-dose).

V_d: Volume of distribution (V_d) was calculated for each participant from observed LNG concentration from LNG PK samples at pre-dose through 48 hours post-dose.

T_{1/2}: T_{1/2} for each participant was calculated from the observed LNG concentration from LNG PK samples at pre-dose through 48 hours post-dose. Assay lower limit of quantification for LNG was 0.025 ng/mL; values < LLOQ were imputed as 0 (if pre-dose) or as 0.0125 (if post-dose).

T_{min}: T_{min} for each participant was time to the minimum observed LNG concentration after the observed dose.

Other AUC: AUC for each participant was from LNG concentrations calculated over 24 or 48 hours and modeled to AUC_{infinity} using the linear up/log down version of trapezoidal rule (i.e., noncompartmental technique). This version of the trapezoidal rule uses linear interpolation between untransformed data up to C_{max}, and between log-transformed data from C_{max} through C_{last}. Assay lower limit of quantification for LNG was 0.025 ng/mL; values < LLOQ were imputed as 0 (if pre-dose) or as 0.0125 (if post-dose).

Time Frame: Intensive LNG PK samples within 30 minutes pre-dose, and 0.5, 1, 1.5, 2, 3, 4, 6, and 8, 24 and 48 hours post-dose [adjusting to appropriate time frame above]

Analysis Population: Participants with PK concentrations over 24 or 48 hours and who took both assigned doses of LNG study treatment and expected doses of ART or TB therapy.

Reporting Groups: A-D

Associated study objectives: Primary Objectives 1 and 2, Secondary Objectives 1 and 2

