4.2.2 Primary PK analysis

In addition to the primary PK analyses described above (calculation of GMR and associated 90% CI on LNG PK parameters), the following supplementary analyses will be conducted to test the robustness of results from this primary analysis (based on the primary PK analysis set):

- 1) Parallel analysis of the per-protocol PK set which excludes participants whose measured perpetrator drug concentration was below the pre-defined threshold.
- 2) Estimation of GMR between non-randomized groups, adjusted for prognostic factors, which may be imbalanced between groups. (Note: adjustment will be performed via normal linear regression modeling on log-transformed PK parameters). (Adjusted

GMRs may also be given for the randomized group comparison so that results presented are parallel and this may be interpreted as adjustment for chance imbalance within a small sample size despite randomization.)

Secondary Objective #3: The outcome to address this objective is AUC_{0-24hr}, and the external comparison groups are the LNG groups as published in Pariditpan Contraception, 2017 (Pharmacokinetics of levonorgestrel and ulipristal acetate emergency contraception in women with normal and obese body mass index), and as results available via clinicaltrials.gov NCT:02689804. Within subgroups defined by normal BMI and obese BMI, the GMR and associated 90% CI for AUC_{0-24hrs} for LNG will be estimated between A5375 Group C (DTG) and this external historical control group. (This analysis will use Satterthwaite calculation of standard error.)

Secondary Objective #5: The outcomes to address this objective including the primary outcome (LNG AUC₀₋₈ hours), as well as the following: C_{max}, and AUC₄₈, C₄₈ (or AUC₂₄ and C₂₄, if too many participants are missing PK parameters at 48 hour). The independent variables include the baseline measurements of body weight including body fat percentage, total weight in kg, and BMI in kg/m². To evaluate the association between these baseline independent variables and the outcome of log-transformed LNG PK parameters, generalized linear regression models will be fit, with additional explanatory variable of LNG dose and perpetrator drug. Geographic region and age will be included for in these models to provide calculation of adjusted GMRs where possible.

5 Report Contents

1. *CONSORT Diagram*
 - a. *Screening and screen failures*
 - b. *Enrollment and eligibility violations*

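### SAP 3.1 sets post-dose LNG values below the 0.025 ng/mL LLOQ to 0.125 in the primary AUC0-8h, which is five times the LLOQ and ten times the value in SAP 3.2.2

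*SAP*

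**What the plan says.** SAP 3.1 (Primary Outcome Measures, Description) states the limit, "Assay lower limit of quantification for LNG was 0.025 ng/mL", and then the rule for the primary AUC0-8h: "values < LLOQ were imputed as 0 (if pre-dose) or as 0.125 (if post-dose".

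SAP 3.2.2 (Secondary LNG PK Parameters) repeats the same limit with a different post-dose value. For Cmin it says "Assay lower limit of quantification for LNG was 0.025 ng/mL; values < LLOQ were imputed as 0.0125". For CL/F, half-life and the other AUCs it says "values < LLOQ were imputed as 0 (if pre-dose) or as 0.0125 (if post-dose".

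Protocol 11.3 (LNG analysis) says only that "Standard noncompartmental techniques will be used to determine these PK parameters" and gives no rule for LNG values below the LLOQ. The one such rule in the protocol concerns drug levels in hair: "Values below the detection limit will be counted as equal to the detection limit".

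**The concern.** A sample reported as below 0.025 ng/mL cannot sensibly be given a value of 0.125. Doing so reverses the order of the data: a measured 0.03 stays at 0.03, while a lower, unquantifiable sample is placed above it.

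The two sections also disagree about the same blood samples. Read literally, a sample below the LLOQ at 0.5 h counts as 0.125 in AUC0-8h and as 0.0125 in AUC0-24h and AUC0-48h. SAP 4.2.2 places these parameters side by side under Secondary Objective 5, where AUC0-8h is modelled along with AUC48 (or AUC24).

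The rule is part of the derivation of the outcome that decides both primary objectives, and it is the only below-LLOQ rule given for that outcome. A programmer who follows 3.1 would code the wrong constant.

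**Working it through.** **1. The figures side by side**

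| Parameter | SAP section | LLOQ (ng/mL) | Post-dose value below LLOQ |
|---|---|---|---|
| AUC0-8h (primary) | 3.1 | 0.025 | 0.125 |
| Cmin | 3.2.2 | 0.025 | 0.0125 |
| CL/F | 3.2.2 | 0.025 | 0.0125 |
| Half-life | 3.2.2 | 0.025 | 0.0125 |
| Other AUCs | 3.2.2 | 0.025 | 0.0125 |

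**2. Can 0.125 be derived from the stated limit?** The usual substitutions are 0, LLOQ/2 = 0.025/2 = 0.0125, LLOQ/√2 = 0.0177, and LLOQ = 0.025. None gives 0.125, and LLOQ/2 reproduces the 3.2.2 value exactly. The ratios are 0.125/0.025 = 5 and 0.125/0.0125 = 10. An LLOQ of 0.25 would give 0.125 as its half, but the SAP states 0.025 all five times.

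**3. Effect of one early sample.** SAP 3.1 samples at 0.5, 1, 1.5 and 2 h and uses the linear trapezoid up to Cmax. A rising-limb sample at 0.5, 1 or 1.5 h has 0.5 h on each side, so its weight is (0.5 + 0.5)/2 = 0.5 h. The change in AUC0-8h is (0.125 − 0.0125) × 0.5 = 0.05625 ng·h/mL.

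**4. Relative to AUC0-8h.** The documents give no AUC0-8h, so a range of 20 to 105 ng·h/mL is assumed:
- 0.05625/20 = 0.28%
- 0.05625/45 = 0.13%
- 0.05625/105 = 0.054%

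An illustrative one-compartment profile gives the same order of size. It assumes ka 1.5/h, an 8 h half-life over the window and an absorption lag of 0.5 or 1 h, which leaves one or two samples below the LLOQ.

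| Cmax (ng/mL) | Source | One sample | Two samples |
|---|---|---|---|
| 19.1 | Protocol 2.1.1 | 0.05% | 0.10% |
| 8.2 | 57% lower, from Protocol 2.2 | 0.11% | 0.24% |
| 2 | assumed low case | 0.46% | 0.98% |

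**5. Effect on the GMR**, with one such sample per affected woman:
- 3 of 30 women in one group, none in the other: exp(0.1 × ln(1 + 0.05625/20)) − 1 = 0.028%; at an AUC of 105, 0.0054%.
- All 30 in one group, none in the other: 0.28% at an AUC of 20; 0.054% at 105.

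**6. Against the planned precision.** At CV 0.45 the log-scale SD is √ln(0.45² + 1) = 0.429. With 30 per group, SE = 0.429 × √(2/30) = 0.111, and the 90% half-width is t(0.95, 58 df) × SE = 0.185. This gives 83% to 120% about a GMR of 100%, which reproduces the interval in SAP 2.3. The all-30 case at an AUC of 20 is ln(1 + 0.05625/20)/0.185 = 0.015, or 1.5% of the half-width.

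**7. A harsher case.** Suppose every woman in one group had two such samples at the assumed Cmax of 2 ng/mL (AUC 11.46). Then ln(1 + 0.1125/11.46)/0.185 = 0.053, about 5% of the half-width.

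**8. A late sample.** An 8 h sample below the LLOQ would matter more. After a 6 h value of 5 ng/mL, the log trapezoid gives 2.64 instead of 1.66 ng·h/mL, a difference of 0.98. Such a fall within 2 h is implausible with the half-lives in Protocol 2.1.1 (about 17 h or longer).

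**The case against.** The strongest reply is that this is a probable dropped zero with almost no numerical consequence. The mean Cmax in Protocol 2.1.1 is 19.1 ng/mL, so the LLOQ is about 0.13% of it (0.025/19.1). Dosing is directly observed, so post-dose samples below the LLOQ within 8 h should be few and confined to the first draws, and there may be none. That stands as to size. It does not make the stated rule correct, because the rule belongs to the primary outcome's derivation and not to background text.

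A second reply is that nothing shows which value the calculation uses. The SAP is worded in the past tense and leaves coding details to an Analysis Implementation Plan that is not among the documents. Editing 3.1 alone could then misdescribe what was done. This is fair, and it is why the code should be checked first. If the code does use 0.125, the remedy is still 0.0125, with a rerun.

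Two lesser points also stand. Secondary Objective 5 lists its PK parameters as separate outcomes, so the two values conflict across models and not within one. The hair rule concerns another matrix and other drugs. It shows only that the protocol nowhere sets a value above the limit, and it does not support 0.0125.

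**Conclusion.** The concern holds. SAP 3.1 states a value that cannot be right for a sample below 0.025 ng/mL, and it contradicts SAP 3.2.2 for the same assay and limit. Neither document reconciles the two. A lost zero in 0.0125 is the likely cause, though the documents do not say so.

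The expected effect is very small: 0.056 ng·h/mL per early sample, and a GMR shift of at most 0.28% even if every woman in one group and none in the other had one such sample. That ceiling assumes one sample per woman at 0.5 to 1.5 h and an AUC0-8h of at least 20 ng·h/mL. Lower exposure or more such samples would raise it, to about 5% of the planned half-width in the harsher case above. The number of samples below the LLOQ is not given. The primary conclusion is not expected to change; the reason to correct the figure is that one assay should have one rule.

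**What to change.** 1. Confirm in the Analysis Implementation Plan, the analysis code or the PK dataset which post-dose value is used for AUC0-8h.
2. Change 0.125 to 0.0125 in SAP 3.1, so that one below-LLOQ rule applies to all LNG parameters.
3. If the code uses 0.125, rerun AUC0-8h and the analyses that depend on it with 0.0125.
4. Check that any registry description taken from SAP section 3 carries the corrected value.

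The cost is a one-digit correction and, at most, a rerun on existing data. No new data are needed, and the design, the trapezoidal method and the GMR analysis stay as they are.
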